5.3.1 Ventilator Protocol Monitoring

Ventilator parameters, pH, and SpO₂ will be recorded daily at randomly selected times to assess for accuracy of the ventilator settings relative to the protocol requirements. The following parameters will be recorded:

1. Ventilator mode
2. Tidal volume
3. Respiratory rate (set)
4. Plateau pressure
5. I:E ratio
6. FiO₂
7. PEEP
8. Corresponding pH and SpO₂, when available.

5.4 Endpoint Determinations

1. Vital status at 28 days.
2. Time of initiation of unassisted breathing.
3. Status 48 hours after initiation of unassisted breathing.
4. Date of ICU discharge.
5. Date of hospital discharge.
6. Vital status at 60 days if still in hospital.

6 Statistical Considerations

The primary objective of this trial is to compare mortality prior to hospital discharge in ALI/ARDS patients who receive a Higher ELV/Lower FiO₂ ventilation strategy versus a Lower ELV/Higher FiO₂ strategy. The Lower ELV/Higher FiO₂ strategy is identical to the 6 ml/kg tidal volume strategy used in the recently completed ARDS Network trial. In this previous study, mortality prior to hospital discharge to 60 days after randomization in the 6 ml/kg tidal volume group was 28%. For this study, it is assumed that mortality prior to hospital discharge to day 60 in the Lower ELV/Higher FiO₂ study group will be 28%. This new study will accrue up to 750 subjects and have an 89% chance of finding a significant mortality benefit of the Higher ELV/Lower FiO₂ strategy if the true difference is 10% or greater (from 28% to 18%) using a one-sided 0.025 significance level test (equivalent to a two-sided $p = 0.05$ significance level).

The trial will be monitored by a Data and Safety Monitoring Board (DSMB). Two interim analyses are planned, after 250 and 500 subjects have completed the trial procedures. The trial may be stopped by the DSMB for futility of the Higher ELV/Lower FiO₂ strategy at the first interim analysis if mortality in the Higher ELV/Lower FiO₂ group is less than that observed in the Lower ELV/Higher FiO₂ group. The trial may be stopped at the second interim analysis if mortality in the Higher ELV/Lower FiO₂ group is not at least 2% better. At each interim analysis, overall mortality will be assessed prior to comparison of the group mortality rates. If the overall mortality is such that the futility boundary

would not maintain at least 90% power to detect an absolute 10% difference in mortality, then the futility boundary will be adjusted. If there is no true difference in mortality between study groups, there is a 50% chance that the trial will stop for futility at the first interim analysis and an additional 24% chance of stopping for futility at the second interim analysis.

The DSMB may stop the trial at each of the interim analyses for efficacy of the Higher ELV/Lower FiO₂ strategy. The criteria for stopping the trial for efficacy are based on an O'Brien-Fleming upper boundary with a one-sided $p = 0.025$ level. The boundary will be lowered slightly to counteract the conservatism of the futility boundary. The boundary is $2.0 * \sqrt{3/i}$, where $i = 1, 2, \text{ or } 3$ corresponding to each of the planned analyses.

The sample size consideration is based on the results of the recently completed ARDS Network trial of 6 ml/kg vs 12 ml/kg tidal volume ventilation and also on the study by Amato et al. [31], which this new study attempts to emulate. In our recently completed study, mortality prior to hospital discharge to day 180 after randomization was 31.3% and 39.8% in the 6 ml/kg and 12 ml/kg study groups, respectively. The mortality rates prior to hospital discharge to day 60 were 29% and 38%, respectively. The difference in mortality prior to hospital discharge to day 60 was the same as the difference in mortality prior to hospital discharge to day 180, which suggests that the frequency of late deaths (after day 60) was not affected by ventilation strategy. A reduction in mortality prior to hospital discharge to day 60 from 28% to 18% in this new study represents a 36% reduction. This is similar but slightly less than that found by Amato et al. ([31]), who found a 46% reduction in mortality at 28 days with a Hi-PEEP strategy.

7 Data Collection and Site Monitoring

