- **Objectives:** To compare clinical outcomes of patients with acute lung injury and acute respiratory distress syndrome treated with a higher end-expiratory lung volume/lower FiO₂ versus a lower end-expiratory lung volume/higher FiO₂ ventilation strategy.
- **Hypothesis (Ho):** Mortality from ALI/ARDS will be the same in patients treated with a higher end-expiratory lung volume/lower FiO₂ ventilation strategy as in patients treated with a lower end-expiratory lung volume/higher FiO₂ ventilation strategy.
- **Study Design:** Multi-Center, prospective, randomized, controlled clinical trial.
 1. Enrollment: approximately 24 months.
 2. Patients will be treated for 28 days or until they achieve unassisted breathing.
 3. Patients will be followed for 60 days or until discharged home with unassisted breathing.
- **Sample Size/Interim Monitoring:**
 1. The study will accrue a maximum of 750 patients.
 2. Progress of the trial will be reviewed by an independent Data and Safety Monitoring Board to determine if randomization should stop for futility, lack of safety, or proven efficacy. Interim analyses will be conducted after completion of the study procedures in approximately 250 and 500 patients. Stopping for futility or efficacy will be based on formal group sequential stopping boundaries.
- **Inclusion Criteria:** Acute Onset of:

1. $\text{PaO}_2/\text{FiO}_2 \leq 300$ (adjusted for barometric pressure).
2. Bilateral infiltrates consistent with pulmonary edema on frontal chest radiograph.
3. Requirement for positive pressure ventilation through an endotracheal tube.
4. No clinical evidence of left atrial hypertension. If measured, pulmonary arterial wedge pressure ≤ 18 mmHg.

● **Exclusion Criteria:**

1. Clinicians caring for patient refuse to use Volume Assist/Control ventilation for at least 12 hours.
2. Age < 13 years.
3. Participation in other intervention trials in ALI, ARDS, or sepsis within the previous 30 days.
4. > 36 hours since all inclusion criteria are met.
5. Neuromuscular disease that impairs ability to ventilate without assistance, such as C5 or higher spinal cord injury, amyotrophic lateral sclerosis, Guillain-Barre syndrome, and myasthenia gravis.
6. Pregnancy (negative pregnancy test required for women of child-bearing potential).

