3.7 Minorities/Women

Gender and racial patient subsets were considered by the NHLBI in selecting the Network Centers. The demographic profiles of the Centers selected for the Network show that the aggregate ALI/ARDS patient population contains representative proportions of minorities (25%) and

women (39%). (Values from 6702 patients with ALI/ARDS in the ARDSnet 01 Screening Logs from March, 1996 - February, 1999). Recruitment of minorities and women will be monitored by the Network Coordinating Center. If necessary, additional recruitment efforts will be made at specific centers to ensure that the aggregate patient sample contains appropriate gender and minority subsets.

Randomization will result in approximately equal numbers of patients assigned to the treatment arms within each population subset. It will be possible to make statistical comparisons within these subsets; however, any inferences derived from these analyses will be of low power because of the relatively small number of patients within the subsets. The primary value of such analyses would be for generating additional hypotheses, which is appropriate given the current lack of evidence of gender or race-related interactions with the treatment interventions in the proposed study.

4 Study Procedures

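### The futility safeguard in Section 6 requires at least 90% power, but the design has 89% at its planning rates, and no change to the futility boundary reaches 90% once overall mortality exceeds about 23%

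*Supplement*

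**What the plan says.** All of this is in Section 6 (Statistical Considerations) unless noted.

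- **Size and power.** "The study will accrue a maximum of 750 patients" (Study Summary). Section 6 says the trial will "have an 89% chance of finding a significant mortality benefit of the Higher ELV/Lower FiO₂ strategy" if mortality falls from 28% to 18%, at one-sided 0.025.
- **Futility rules.** The first look comes after 250 patients. The trial may stop there if mortality is higher in the Higher ELV group (direction as given in the correction notice at the front of the protocol). At 500 patients it may stop if that group is not at least 2 points better.
- **Safeguard.** Overall mortality is assessed before the groups are compared. If the futility boundary "would not maintain at least 90% power to detect an absolute 10% difference in mortality, then the futility boundary will be adjusted". No other remedy is named.
- **Null behaviour.** With no true difference, "there is a 50% chance that the trial will stop for futility at the first interim analysis and an additional 24% chance" at the second.
- **Efficacy boundary.** 2.0 × √(3/i) at looks i = 1, 2, 3.
- **Prior-trial rate.** Mortality to day 60 "in the 6 ml/kg tidal volume group was 28" per cent. Two paragraphs later, for the 6 and 12 ml/kg groups: "The mortality rates prior to hospital discharge to day 60 were 29% and 38%, respectively".

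**The concern.** The stated power (89%) is already below the level the safeguard requires (at least 90%), and both refer to a 10-point difference. The safeguard is therefore triggered if the trial goes exactly as planned.

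The remedy also has a limit. Changing the futility boundary can only give back the power that the boundary costs. If the design without any futility rule falls short of 90%, no adjustment can meet the condition, and the maximum sample size is fixed.

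What is at stake is the rule the DSMB applies before it sees the group comparison. If the target is out of reach, the board has to decide at the interim, without guidance, how far to move the boundary. The quoted 50% and 24% would then not describe the boundary in use.

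**Working it through.** **Inputs.** Up to 750 patients (Study Summary). Equal arms: Section 3.7 says "Randomization will result in approximately equal numbers of patients assigned to the treatment arms". This gives 125, 250 and 375 per arm at the three looks. Efficacy limits: 2.0√(3/1) = 3.46, 2.0√(3/2) = 2.45, 2.0√(3/3) = 2.00. Futility: observed benefit below 0 at look 1 or below 2 points at look 2, treated as binding. Overall mortality p with a 10-point difference is taken as p + 5 versus p − 5 points, so 28% versus 18% is 23% overall.

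**Method.** Let d be the observed benefit and n the number per arm at a look. The test statistic is z = d / √(2p̄(1−p̄)/n). Power is the chance that z crosses an efficacy limit before a futility stop. It was computed from the joint normal distribution of the three looks (pooled and unpooled variance) and checked by simulating 1,000,000 binomial trials.

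**Step 1: reproduce the plan's figures.**
- Power at 28% versus 18% with the stated futility rules: 88.5% (pooled), 88.7% (unpooled), 88.9% (binomial). The plan says 89%.
- No difference, 28% in both arms, normal theory: futility stop 50.0% at look 1 and 23.9% at look 2. The plan says 50% and 24%. Binomial simulation gives about 47% and 25%, because exact ties do not count as worse.

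So this is the plan's design, and its 89% already includes the cost of the futility rules.

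**Step 2: power by overall mortality.** Normal theory, pooled to unpooled:

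| Overall mortality | Stated boundary | No futility boundary |
|---|---|---|
| 21% | 90.4-90.6% | 91.8-92.0% |
| 22% | 89.4-89.6% | 90.9-91.1% |
| 23% (28 vs 18) | 88.5-88.7% | 90.0-90.2% |
| 24% (29 vs 19) | 87.6-87.8% | 89.1-89.4% |
| 25% | 86.7-86.9% | 88.3-88.5% |
| 28% (33 vs 23) | 84.2-84.5% | 85.9-86.2% |
| 30% | 82.7-83.0% | 84.4-84.7% |

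Binomial simulation, with and without the boundary: 28/18, 88.9% and 90.1%; 29/19, about 88.1% and 89.3%; 33/23, about 84.6% and 86.1%.

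The stated boundary crosses 90% at about 21.5% overall (21.4-21.9% by method). The design without futility crosses it at about 23.0-23.4%.

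**Step 3: check the ceiling by hand.** A single test at z = 1.96 with 375 per arm and no interim looks has power Φ((0.10 − 1.96·SE₀)/SE₁).
- 28/18: SE₀ = √(2·0.23·0.77/375) = 0.03073; SE₁ = √((0.28·0.72 + 0.18·0.82)/375) = 0.03052; Φ(0.03976/0.03052) = Φ(1.303) = 90.4%.
- 29/19: SE₀ = 0.03119, SE₁ = 0.03098; Φ(1.255) = 89.5%.
- 33/23: SE₀ = 0.03279, SE₁ = 0.03259; Φ(1.097) = 86.4%.

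Even with no monitoring at all, 750 patients do not give 90% at 24% overall.

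**Step 4: can a loosened boundary meet 90% at 23%?** Just. Suppose the trial stops only if the Higher ELV group is more than 4 points worse at look 1, or worse at all at look 2. The binomial simulation then gives 90.1% power at 28/18 and still about a 51% chance of a futility stop with no difference at 28%. The margin depends on the method, since the pooled normal calculation puts the ceiling itself at 90.0%.

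**The case against.** **It is a trigger, not a promise of power.** This is right. The clause does not guarantee 90% final power, and a board whose trigger fires can still do what the text says and loosen the boundary. What it cannot always do is reach the level that defines the trigger, and the plan is silent about that case.

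**The futility rules are permissive.** The trial may be stopped; it need not be. If the board never acts on futility, power at 28/18 is about 90%. That explains the one-point gap at 23% overall. It does not help at higher mortality, where the design without futility is also short.

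**The 90% may be loose rounding of 89%.** That is plausible at 23% overall. It does not cover 84-86% at 28% overall.

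**The 90% may mean the chance of not stopping for futility under a 10-point benefit.** On this reading there is no contradiction: the chance is about 96% at 23% overall and 93% at 40%. But the rule would then never fire across that range, and the text speaks of power to detect a difference. It is the weaker reading.

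**Stronger readings the documents do not support.**
- A reader might infer that the rule cannot be followed at all, or that at the planning rates only removing the boundary would do. Below about 21.5% overall it is met unchanged, and Step 4 shows a loosened boundary that just meets it at 23%.
- A reader might infer that the boundary is abandoned when there is no benefit. The text says adjusted, and the 50% and 24% are most naturally read as properties of the boundary as stated.
- A reader might infer from the 29% that the planning rate is wrong. Section 6 makes 28% an explicit assumption ("it is assumed that mortality prior to hospital discharge to day 60 in the Lower ELV/Higher FiO₂ study group will be 28" per cent), and a planning rate need not equal a prior result.

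**Conclusion.** The point stands in a limited form. Three ranges of overall mortality need to be kept apart:

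- below about 21.5%, the stated boundary meets the 90% condition;
- from about 21.5% to about 23%, only a looser boundary meets it, and barely so at 23%;
- above about 23.0-23.4%, nothing done to the futility boundary meets it with 750 patients.

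The plan's own scenarios fall at the edge of the last range or inside it: 23% overall if the benefit is real, and 28% if there is none, where the ceiling is about 86%. The shortfall is about 1 point at the planning rates and about 4 points at 28% even with futility removed.

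The efficacy test is not affected: one-sided type I error is about 0.024-0.025 with or without the futility rules. The harm is an interim rule whose threshold the design does not deliver, with no stated fallback.

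This rests on equal arms, looks at exactly 250, 500 and 750 patients, the unchanged efficacy boundary, and futility treated as binding for the with-boundary figures. The 28% and 29% given for the same prior-trial rate are a separate, smaller inconsistency.

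**What to change.** 1. Replace the 90% condition with one the design can meet. One form is a stated maximum loss of power, at the observed overall mortality, relative to the same design without futility; the present boundary costs about 1.2-1.7 points over the range tabulated. Another is a lower power floor; to be attainable up to 30% overall mortality it would have to lie below about 84.4%. The documents do not settle which form or value to use, so the sponsor should choose and justify it.
2. State what the DSMB does when the target cannot be reached.
3. Say whether power is computed with the futility rules as binding or as advisory.
4. Give the DSMB a table of the boundary and its power for overall mortality from 20% to 30%.
5. State that the 50% and 24% stopping chances apply to the unadjusted boundary, with 28% mortality in both groups.
6. Separately, reconcile the 28% and 29% given for the prior trial's 6 ml/kg group at day 60. If 29% is adopted for planning, power at 29% versus 19% is about 88%.

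The cost is a rewording of Section 6 and one table, ideally before the first interim analysis. No patients are added and the efficacy boundary does not change.

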7.1 Data collection

The research coordinators will enter data on a web-based electronic data capture system. Software is designed with a series of checks to avoid missing or incorrect data.

7.2 Reporting of adverse events

Investigators at each site will determine daily if any clinical adverse experiences occur during the period from when the initial ventilator changes are made to 48 hours after initiating unassisted breathing or day 60, whichever occurs first. The investigator will evaluate any changes in laboratory values and physical signs and will determine if the change is clinically important and different from what is expected in the course of treatment of patients with ALI or ARDS. If clinically important and unexpected adverse experiences occur, they will be recorded on the adverse event case report form.

Investigators will report all serious, unexpected, and study-related adverse events, as defined in Appendix B, to the Clinical Coordinating Center within 24 hours. The local Institutional Review Board will also be informed in a timely manner. The investigator will then submit a detailed written report to the Clinical Coordinating Center no later than 5 days after the investigator discovers the event.

The Clinical Coordinating Center will report all serious, unexpected, and study-related adverse events to the FDA or DSMB within 10 working days and will distribute these reports to investigators for submission to their respective Institutional Review Boards. The DSMB will also review all adverse events during scheduled interval analyses. The Clinical Coordinating Center will distribute the written summary of the DSMB's periodic review of adverse events to investigators for submission to their respective Institutional Review Boards in accordance with NIH Guidelines.

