- 4 Number of Organ Failure Free days at 28 days after randomization, using previously validated definitions for renal, central nervous, coagulation, circulation, and hepatic organ and system failures [35], [36].
- 5 Number of days between the day of first meeting criteria to commence-weaning and day 28 after randomization.
- 6 Number of days between the day of initially achieving unassisted ventilation and day 28 after enrollment.
- 7 Incidence of barotrauma (pneumothoraces, pneumatoceles > 2 cm largest diameter, pneumomediastinum).
- 8 Percentage of patients discharged alive from hospital. Patients alive in hospital at 60 days will be considered to have been discharged alive.
- 9 Mortality and days of unassisted breathing with pre-randomization $\text{PaO}_2/\text{FiO}_2 \leq 200$.

3 Study Population and Enrollment

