If criteria 1-5 are met for > 120 minutes, unassisted breathing will continue (step 4.1.2.6). If any of criteria 1-5 are not met during the 120 minute trial, then PS will resume at 5 cmH₂O and tolerance will be reassessed (step 4.1.2.3).

4.1.2.6 Definition of unassisted breathing.

1. Extubated with face mask, nasal prong oxygen, or room air, OR
2. T-tube breathing, OR
3. Tracheostomy mask breathing, OR
4. CPAP = 5 without PS or IMV assistance.

4.1.3 Completion of ventilator procedures.

Patients will be considered to have completed the study ventilator procedures if any of the following conditions occur:

1. Death.
2. Hospital discharge.
3. Alive 28 days after randomization.

If a patient requires positive pressure ventilation after a period of unassisted breathing, the study ventilator procedures for the group to which the patient was randomized will resume unless the patient was discharged from the hospital or > 28 days elapsed since enrollment.

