5.2 Baseline Assessments

The following information will be recorded during the four-hour interval that precedes initial protocol ventilator changes (if any). Parameters indicated with "*" will be measured during the four-hour interval. If more

than one value is available during the four-hour interval, the last value will be recorded. For other parameters, most recent values will be recorded. If no values are available during the preceding 24 hours, then values will be measured during the four-hour interval prior to initial ventilator changes (if any).

1. * Vital Signs: heart rate (b/min), systolic and diastolic BP (mmHg), body temperature (°C), total respiratory rate.
2. *Ventilator Parameters: Mode, ventilator rate, tidal volume (inspired), FiO₂, PEEP, plateau pressure (0.5 second pause), ventilator manufacturer and model.
3. Measured body weight (kg).
4. Arterial PO₂, PCO₂, and pH and SpO₂.
5. Urinary output (most recent 24 hour value).
6. Serum electrolytes, BUN, creatinine and glucose.
7. Blood hematocrit, WBC, and platelets.
8. Serum albumin concentration.
9. * Blood for cytokines, mediators, and markers of lung injury. Plasma obtained from two, 10 ml EDTA anticoagulated blood samples will be divided immediately after centrifugation into 12 equal 1 ml aliquots in specified tubes and frozen at -70°C.
10. *Glasgow coma score.
11. Frontal chest radiograph (when available):
 - (a) Radiographic Lung Injury Score ([33], # of quadrants)
 - (b) Presence/absence of barotrauma:
 - i. pneumothoraces (R/L)
 - ii. pneumomediastinum
 - iii. pneumatocelles > 2 cm minimum diameter (R/L)
 - iv. subcutaneous emphysema
12. Administration of the following medications (Y/N):

- (a) Sedatives
- (b) Neuromuscular blocking agents
- (c) Vasopressors (maximum number given simultaneously)
- (d) Corticosteroids (dose ranges)
- (e) Buccal smear for genetic analysis in patients who have consented to genetic testing.

Most recent values for the following additional parameters will be recorded only if they are available from clinically required measurements.

13. Pulmonary artery systolic, diastolic, mean and pulmonary artery occlusion pressures, central venous pressure, and cardiac index.

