5.3 Assessments During Enrollment

The following data will provide the basis for assessing protocol compliance and safety as well as between-group differences in several efficacy variables. Data for each of the variables will be recorded on the days shown in the Time-Events schedule (Appendix C) or until death, discharge from intensive care unit, or unassisted ventilation for 48 hours.

Reference Measurements

The following parameters will be measured and recorded between 0600 and 1000 on the days specified in the Time-Events schedule (Appendix C). The following conditions will be ensured prior to measurements: supine position for 15 minutes; no endobronchial suctioning for 10 minutes; no invasive procedures or ventilator changes for 30 minutes. SpO₂ sensors will be checked for optimal position, cleanliness, and consistent readings with satisfactory waveforms, if displayed. SpO₂ values will be observed for 1 minute and a representative value recorded. All vascular pressures will be zero-referenced to the mid-axillary line.

1. If receiving positive pressure ventilation:
 - (a) Ventilator mode
 - (b) Ventilator set inspired tidal volume (if on volume cycled mode)

- (c) Pressure Support level (if on PS for weaning)
 - (d) Total respiratory rate
 - (e) Total minute ventilation
 - (f) PEEP
 - (g) Plateau pressure (if on volume cycled mode)
 - (h) Peak inspiratory pressure (if on volume cycled mode)
2. FiO₂
 3. SpO₂ on current FiO₂
 4. Hemodynamic values
 - (a) Arterial systolic, diastolic and mean pressures
 - (b) Heart Rate (beats/min)

Values for the following variables will be recorded for the dates shown in the Time-Events Schedule. If the measurements are not obtained during the 4-hour reference interval, then the value obtained closest in time to the reference interval on the respective date will be recorded. If more than one value is obtained during the reference interval, then the earliest value during the interval will be recorded.

5. Weight (kg), using same technique for each measurement (bed-scale vs lift vs other)
6. Blood hemoglobin concentration
7. Arterial PO₂, PCO₂, and pH and calculated bicarbonate concentrations
8. Requirements for the following medications (Y/N):
 - (a) Sedatives and tranquilizers
 - (b) Neuromuscular blocking agents
 - (c) Vasopressors (maximum number given simultaneously)
 - (d) Experimental treatments: nitric oxide, fluorocarbons, surfactants, extracorporeal gas exchange (ECMO, ECCO2R, etc.)

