1. In the Higher EELV/Lower FiO₂ study group, the following three FiO₂/PEEP combinations are deleted from the low-end of the FiO₂/PEEP scheme: .30/5, .30/8, .30/10.
2. Clause (b), first sentence: "FiO₂/PEEP setting may not be decreased from its initial level ... in the Higher ELV/Lower FiO₂ group for at least 12 hours after initial protocol ventilator adjustments" is amended to read as follows:
 - (b) FiO₂/PEEP setting may not be decreased below .30/14 in the Higher EELV/Lower FiO₂ group (except for possible weaning as described in the subsequent amendment to section 4.1.2.1.2) during the first 48 hours after initial protocol ventilator adjustments. FiO₂/PEEP setting may not be decreased below .30/12 in the Higher EELV/Lower FiO₂ group (except for possible weaning as described in the subsequent amendment to section 4.4.2.1.2) after 48 hours until 28 days elapse from initiation of protocol ventilator procedures.

II. Page 25, Section 4.1.2.1.2 is amended as follows to allow both study groups to begin to wean if arterial oxygenation can be maintained at or above the target range on FiO₂/PEEP of .40/8. This amendment supercedes a previous amendment dated January 14, 2000:

2. Lower EELV/Higher FiO₂ Group: FiO₂/PEEP ≤ .40/8.

Higher EELV/Lower FiO₂ Group:

- From 12-48 hours after initiation of protocol ventilator procedures: If FiO₂ ≤ .30 and PEEP = 14, FiO₂/PEEP will be changed to .40/8. SpO₂ must remain ≥ 88% for 30 minutes at FiO₂/PEEP = .40/8. If SpO₂ falls below 88%, previous FiO₂/PEEP settings will be resumed. (Recruitment Maneuvers will be conducted as defined in Section 4.1.1 after returning to previous FiO₂/PEEP settings if SpO₂ < 88% during the trial at FiO₂/PEEP = .40/8).
- 48 hours-28 days after initiation of protocol ventilator procedures: If FiO₂ ≤ .30 and PEEP = 12, FiO₂/PEEP will be changed to .40/8. SpO₂ must remain ≥ 88% for 30 minutes at FiO₂/PEEP = .40/8. If SpO₂ falls below 88%, previous FiO₂/PEEP settings will be resumed. (Recruitment Maneuvers will be conducted as defined in Section 4.1.1 after returning to previous FiO₂/PEEP settings if SpO₂ < 88% during the trial at FiO₂/PEEP = .40/8).

The following addition in **bold face type** is a clarification of intent of the July 20, 1999 Version I of the protocol

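### Adverse-event and barotrauma recording is not clearly required once assigned ventilation resumes after unassisted breathing, and the pneumatocele item on the radiograph form does not match outcome 7

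*Supplement*

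**What the plan says.** **Treatment.** Section 4.1.3 ends the study ventilator procedures at death, at hospital discharge, or when the patient is "Alive 28 days after randomization". Unassisted breathing is not on that list. If positive pressure is needed again, "the study ventilator procedures for the group to which the patient was randomized will resume", unless the patient has left hospital or more than 28 days have passed. The May 15, 2000 amendment (item I, clause b) is consistent with this: its later lower limit on the FiO₂/PEEP setting in the Higher ELV group applies "after 48 hours until 28 days elapse from initiation of protocol ventilator procedures", apart from weaning.

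**Adverse events.** Section 7.2 sets the daily determination to run from when "initial ventilator changes are made to 48 hours after initiating unassisted breathing or day 60, whichever occurs first". Appendix B instead calls for record review and case-report-form reporting of all adverse events throughout the study period, a term it does not define.

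**Barotrauma.** It is secondary outcome 7 (Study Summary and Section 2), with no time window, and it is not among the endpoint determinations in Section 5.4. It is read from the chest radiograph under Section 5.3, item 9. Data under that section are recorded on the Appendix C days "or until death, discharge from intensive care unit, or unassisted ventilation for 48 hours".

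**Definition.** Outcome 7 counts "pneumatoceles > 2 cm largest diameter". The baseline radiograph item (Section 5.2, item 11) records "pneumatocelles > 2 cm minimum diameter", and Section 5.3 item 9 reuses the baseline description.

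No amendment shown changes any of these recording rules.

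**The concern.** The treatment window and the recording windows end on different events. Assigned ventilation can restart up to day 28. Recording closes around the time of liberation, and nothing in 7.2 or 5.3 reopens it. The protocol foresees relapse, since the ventilator-free-day rule in Section 2 deals with it explicitly, but the safety windows do not.

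Two consequences follow. First, a patient can be exposed again to the strategy under test at a time when the operative recording sections do not clearly ask for adverse events or barotrauma. Second, time to liberation is a post-randomization event that the strategies may change, so the arms may be observed for different lengths of time. A comparison of barotrauma incidence then mixes risk with duration of observation. The DSMB also reviews adverse events at its interim reviews, so a gap would carry through to oversight.

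The diameter mismatch is a separate matter and is not confined to patients who relapse. The form's wording is narrower than the outcome it is meant to supply.

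**Working it through.** The plan gives no figure for re-ventilation or for missed events, so there is nothing of its own to reproduce here. The check compares the windows, then does day arithmetic, then gives an illustrative count.

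**1. Windows side by side**

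| Rule | Ends at | Restart clause |
|---|---|---|
| Assigned ventilation (4.1.3) | death, hospital discharge, day 28 | yes, on re-ventilation |
| Adverse events (7.2) | 48 h after initiating unassisted breathing, or day 60 if earlier | none |
| Barotrauma and other 5.3 data | Appendix C days, or until death, ICU discharge or 48 h unassisted | none |
| Adverse events (Appendix B) | end of an undefined study period | not addressed |

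**2. Days outside the 7.2 window.** Let unassisted breathing begin on day d. The window closes on day d + 2, so the time in which assigned ventilation could still be in use outside it is at most 28 − (d + 2) = 26 − d days.

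- d = 5: 21 days
- d = 10: 16 days
- d = 16 (the day used in the ventilator-free-day example in Section 2): 10 days
- d = 20: 6 days
- d = 26: 0 days

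These are upper limits on possible exposure, not expected durations.

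**3. The two recording rules are not the same.** Take d = 10.

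- Re-ventilated on day 11: 48 hours unassisted has not been reached, so Section 5.3 recording continues unless the patient leaves the ICU. The 7.2 clock runs from initiation and, read literally, still expires on day 12.
- Re-ventilated on day 15 after sustained unassisted breathing: both rules have closed, and assigned ventilation may run for up to 28 − 15 = 13 days.

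**4. Illustrative count.** Assume that 60-70% of the 750 patients achieve 48 hours unassisted and that 5-15% of those are re-ventilated by day 28. Neither rate is in the documents.

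- Low: 750 × 0.60 × 0.05 = 22.5, about 22
- High: 750 × 0.70 × 0.15 = 78.75, about 79

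This counts patients, not missed events. It leaves out those re-ventilated before completing 48 hours, for whom only the 7.2 clock is in question.

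**5. Diameter.** A pneumatocele of 3 × 1.5 cm has a largest diameter above 2 cm and a minimum diameter below it. It meets outcome 7 but not the form item. The lesions lost are those with largest diameter above 2 cm and minimum diameter not above 2 cm.

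**The case against.** The best reply is that adverse events are covered elsewhere. Appendix B's review and reporting duties are not tied to unassisted breathing, and the 24-hour duty for serious, unexpected, study-related events carries no 48-hour limit. This stands to the extent that a reader who infers that later harms simply go unrecorded goes further than the documents allow. It does not close the gap. The study period is undefined, so sites have two rules with different end dates. The expedited route requires the event to be unexpected, and Section 1.1 already names barotrauma as a risk of higher PEEP, so it may well be classed as expected. The Section 7.2 form likewise takes only clinically important and unexpected experiences. Barotrauma therefore rests mainly on Section 5.3.

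Second, 7.2 does not say that the first initiation of unassisted breathing governs. That is the natural reading, but the text could be taken to start again with a later episode. This is fair, and it is a reason to state the rule.

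Third, Section 5.3's link between the scheduled days and its stopping events is ambiguous, and the Appendix C table is not shown in the text reviewed. Amendment 4 shows that at least one item, the coma score, had been scheduled on fixed days to day 28. The schedule might therefore prompt some later radiograph reading, and a complete absence of barotrauma capture is not established.

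Fourth, death before discharge to day 60 and the loss of ventilator-free days on re-ventilation are captured in any case. This is correct. The point concerns adverse events and barotrauma only.

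A reader might also take barotrauma to be the chief harm the protocol attributes to higher PEEP. The documents do not rank it so: Section 1.1 puts circulatory depression first and pairs barotrauma with stretch injury, and the Risk Assessment does not name it.

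**Conclusion.** The mismatch is real and no amendment shown mends it. Assigned ventilation can resume to day 28, while 7.2 and 5.3 close earlier without a restart clause and Appendix B conflicts with 7.2. Adverse events and barotrauma during resumed assigned ventilation are not reliably required to be recorded, and the observation window depends on time to liberation.

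The number of patients affected cannot be computed from the documents. The range of about 22-79 of 750 rests wholly on the assumed rates above and should not be read as a count of missed events. A difference in observation time between arms is possible, but neither its direction nor its size can be derived, so a claim that the safety comparison is biased one way is not supported.

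The diameter discrepancy stands on the wording alone. Followed as written, the form omits pneumatoceles that outcome 7 counts. It touches one of that outcome's three components, and its frequency is unknown.

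**What to change.** Reconcile Sections 7.2, 5.3, 4.1.3 and Appendix B to one recording period.

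- **7.2:** state that the period reopens whenever study ventilator procedures resume, that the 48 hours run from the latest start of unassisted breathing, and when recording finally ends.
- **Appendix B:** define the study period as that same period.
- **5.3:** state that barotrauma recording restarts on resumption, for example to day 28, and make clear how the scheduled days and the stopping events combine.
- **Outcome 7:** state the matching window.
- **Radiograph form (5.2 item 11, reused in 5.3 item 9):** use the outcome's largest-diameter definition.

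The cost is amendment wording and a few more form-days for re-ventilated patients. Sample size, significance level, power and clinical care are unchanged. One limit remains: a period that reopens with ventilation matches recording to exposure but does not equalize observation time between arms, so the report should state the window over which barotrauma was observed.
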